#### 254 **1.1.2.1 Background on the Guardian-RT**

255 The Guardian-RT was developed and is distributed by Medtronic Minimed. This sensor uses a  
256 glucose oxidase based electrochemical sensor which generates 2 electrons for each glucose  
257 molecule oxidized. The current generated from measuring glucose is called the ISIG (Input  
258 SIGnal). The Guardian-RT system is designed to measure blood glucose levels in a range of 40-400  
259 mg/dl. The sensor is inserted subcutaneously and measures interstitial glucose. When functioning  
260 properly, the Guardian-RT acquires glucose values every 10 seconds and these values are averaged  
261 in the monitor to provide a reading every 5 minutes (or 288 readings a day) which is transmitted  
262 wirelessly to a receiver that can be kept up to 6 feet from the transmitter. Each sensor is designed to  
263 measure readings for up to 72 hours.

264

265 The Guardian-RT has alarms for hypoglycemia and hyperglycemia that can be adjusted by the user.  
266 Subjects can enter events, such as when they took insulin, ate, or exercised. The sensor requires at  
267 least 2 capillary glucose readings each day (every 12 hours) to validate sensor function and allow  
268 for development of a calibration equation. These calibration measurements are performed with a  
269 home glucose meter, and calibration is dependent upon the subject entering glucose values correctly  
270 into the sensor.

271

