478 glucose at the discretion of the investigator.

479  
480 **3.3 Subcutaneous Insulin Infusion Test**

481 Subjects will have a subcutaneous insulin infusion test performed in the morning following the  
482 overnight admission at approximately 8:00 a.m.

483  
484 Prior to starting the test, a HypoMon® (AiMedics Ltd, Sydney, Australia) may be placed around the  
485 subject's chest using an adjustable strap. This monitor, which is about the size of a remote control,  
486 uses wireless technology to pick up skin impedance and ECG signals from a thin belt strapped  
487 around the subject's chest.

488  
489 The glucose concentration as measured by the study HGM must be  $\geq 110$  mg/dL to start the test.  
490

491 At the start of the test, the basal insulin rate will be increased by approximately 25-50% to provide a  
492 gradual decline in blood glucose. A small priming bolus dose of insulin equal to approximately one  
493 hour of the subject's usual basal dose may also be given at the discretion of the investigator in  
494 addition to the 25-50% increase in the basal insulin.

495  
496 The basal insulin rate may be increased an additional amount and additional bolus insulin doses  
497 may be given at the discretion of the investigator in order to get a gradual decline in the glucose  
498 concentration.

499  
500 The test is expected to last approximately 1.5 to 2 hours. If the subject has not reached the endpoint  
501 (<60mg/dL) within 3 hours, the test will be stopped at the discretion of the investigator.

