## 956 **7.2.2 Continuous Glucose Monitor (CGM) Data**

### 958 **7.2.2.1 Glycemic Indices**

959 Analyses based on the Guardian RT will be based on 5 minute readings.

960  
961 Multiple sensor values  $<70$  mg/dL within 30 minutes will be considered a single hypoglycemic  
962 episode. Similarly, multiple values  $>200$  mg/dL within 30 minutes will be considered part of the  
963 same hyperglycemic episode.

964  
965 The following glycemic indices to be calculated for each subject:

- 966 • Mean glucose.

- 967 • Percentage of readings between 70-180 mg/dL.
- 968 • Hypoglycemia:
  - 969 ➤ Percentage of readings < 70, 60, 50 and 40 mg/dL.
  - 970 ➤ Area over the curve (a composite measure of percentage and severity of sensor
  - 971 values  $\leq 70$ mg/dL), defined as the area between the glucose curve and 70 mg/dL.
  - 972 ➤ Number of hypoglycemic episodes (as defined above) per 24 hours.
- 973 • Hyperglycemia:
  - 974 ➤ Percentage of readings > 180, 200, 250 and 300 mg/dL.
  - 975 ➤ Area under the curve (a composite measure of percentage and severity of sensor
  - 976 values >200mg/dL), defined as the area between 200 mg/dL and the glucose curve.
  - 977 ➤ Number of hyperglycemic episodes (as defined above) per 24 hours.

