### 979 7.2.2.2 Accuracy

980 Laboratory glucose measurements will be used as the reference during the CRC Admission for  
 981 determination of the accuracy of the Guardian-RT. The subject's glucose meter (excluding values  
 982 used to calibrate the sensor) will be used as the reference during home use of the Guardian RT.  
 983 Sensor readings will be paired to reference values within  $\pm 2.5$  minutes. For each pair the following  
 984 difference measures will be calculated:

- 985 • Difference – Sensor minus reference value.
- 986 • Absolute Difference – Absolute value of the Difference.
- 987 • Relative Difference – Difference divided by the reference value.
- 988 • Relative Absolute Difference – Absolute value of the Relative Difference.
- 989 • ISO criteria – Sensor within  $\pm 15$  mg/dL if reference  $\leq 75$  mg/dL, or sensor within  $\pm 20\%$  if  
 990 reference >75 mg/dL).

991 Percentiles will be given for the four difference measures and the percentage of pairs meeting the  
 992 ISO criteria will be calculated. Results will be given separately for inpatient and outpatient data.  
 993 Values will be given overall and stratified by reference glucose, age group, gender, HbA1c and  
 994 BMI percentile. A Bland-Altman plot will be constructed. Confidence intervals and comparisons  
 995 of subgroups will use the bootstrap to account for correlated data from the same subject.  
 996

997  
 998 For each subject the glycemic excursion during the subcutaneous insulin infusion test will be  
 999 calculated separately for the reference and sensor values. This will be defined as the baseline minus  
 1000 the nadir glucose value. For the Guardian-RT, the nadir will be taken over the period from baseline  
 1001 to 60 minutes following completion of the subcutaneous insulin infusion test.

1002  
 1003 A scatterplot and Bland-Altman plot will be constructed to compare reference vs. CGM measured  
 1004 glucose drops during the subcutaneous insulin infusion test. Median values and quartiles will be  
 1005 given for each of the difference measures defined above. To investigate potential sensor lag, a  
 1006 scatterplot will be also constructed comparing the CGM vs. reference nadir times (defined as  
 1007 minutes from baseline). Summary statistics will be given for the difference of these two values.  
 1008

1009 A similar analysis will be done for the rise in glucose during the post-dinner blood draws described  
 1010 in section 4.2.

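### The sensor's glucose drop uses the lowest of about 31-37 noisy readings, which makes it larger than a time-matched sensor drop and can partly mask lag in the comparison with the reference

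*Protocol*

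**What the plan says.** Section 7.2.2.2 takes central laboratory glucose as the inpatient reference. The excursion during the insulin infusion test is "calculated separately for the reference and sensor values. This will be defined as the baseline minus" the nadir. A nadir window is stated for the sensor only: "For the Guardian-RT, the nadir will be taken over the period from baseline" "to 60 minutes following completion of the subcutaneous insulin infusion test". The two drops are then compared by scatterplot, Bland-Altman plot, medians and quartiles. Section 7.2.2.1 adds "Analyses based on the Guardian RT will be based on 5 minute readings".

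The same section has two other relevant analyses. The general accuracy analysis matches in time: "Sensor readings will be paired to reference values within" ±2.5 minutes. Possible lag is examined by comparing sensor and reference nadir times.

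On test length, section 3.3 says "The test is expected to last approximately 1.5 to 2 hours", and a test that has not reached the endpoint "within 3 hours, the test will be stopped at the discretion of the investigator". Section 3.3.1 schedules laboratory samples at baseline, at <90, <80, <70 and <60 mg/dL, and 15 minutes after intravenous glucose. Table 5.1 budgets six draws for the test.

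**The concern.** The two nadirs are different kinds of quantity. The reference nadir is in effect a single precise measurement, taken when the test stops. The sensor nadir is an extreme picked from a dense, noisy series. The lowest of many noisy readings lies on average below the sensor's own reading at the true low point, even if the sensor is right on average. Nothing in section 7.2.2.2 smooths the sensor curve or matches sampling times for this comparison.

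Lag works the other way: a sensor that trails a falling glucose shows too small a drop. The drop comparison therefore mixes two errors of opposite sign. Close agreement could reflect an accurate sensor, or lag offset by noise. An apparent overshoot could be noise alone. Secondary objective 3 is sensor accuracy during hypoglycemia, and this is the per-subject display of it.

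**Working it through.** **1. Readings in the sensor window.** Section 1.1.2.1 describes values averaged "in the monitor to provide a reading every 5 minutes (or 288 readings a day) which is transmitted" to the receiver; 1440/5 = 288, which agrees. Counting both ends, the number of readings is (test length + 60)/5 + 1:

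- 90-minute test: 150/5 + 1 = 31
- 120-minute test: 180/5 + 1 = 37
- 180-minute test: 240/5 + 1 = 49

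These counts run from the insulin increase, which is baseline in the synopsis (section 1.3). If baseline is the 95-110 mg/dL sample of section 3.3.1, the window is shorter; a 75-minute fall from there gives 135/5 + 1 = 28.

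**2. Samples behind the reference nadir.** One baseline time, four thresholds and one post-treatment sample make 1 + 4 + 1 = 6, matching Table 5.1. The synopsis allows extra samples while glucose is above 100 mg/dL, but these cannot be the nadir in a test that reaches <60.

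**3. Ceiling on the effect.** If all readings were independent around one level, the expected minimum would lie about 2.06 SD below it for 31 readings and 2.13 SD for 37, against about 1.3 SD for 6. On a curve that falls and recovers the effect is smaller, hence the simulation.

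**4. Simulation against the reference.** Assumptions, none of them in the protocol: linear fall from 110 to 58 mg/dL over 90 minutes (drop 52), recovery to 80-120 mg/dL over 10 minutes, first-order lag, AR(1) sensor noise, laboratory SD 1.5 mg/dL. Mean sensor drop minus reference drop, in mg/dL, with a 10-minute lag:

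| Noise SD | Autocorrelation | Windowed minimum | Read at reference nadir |
|---|---|---|---|
| 0 | - | -5.7 | -5.7 |
| 5 | 0.7 | -4.7 | -5.7 |
| 5 | 0.95 | -5.7 | -5.7 |
| 10 | 0 | +2.6 | -5.9 |
| 10 | 0.7 | -0.8 | -5.4 |
| 10 | 0.95 | -5.2 | -5.9 |
| 15 | 0.7 | +4.0 | -5.9 |
| 15 | 0.95 | -4.1 | -6.1 |

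The matched column stays near the noise-free shortfall of 5.7 whatever the noise. The windowed column moves with the noise: at SD 10 and autocorrelation 0.7 the shortfall shows as only 0.8. With no lag at SD 10 the windowed drop exceeds the reference by 7.3, 3.5 and 0.6 at autocorrelation 0, 0.7 and 0.95, while the matched drop is about right. Over lags of 0-15 minutes and tests of 90 and 120 minutes, the windowed error runs from about -9 to +16.

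**5. Inflation over the matched sensor drop.** With lag 0 or 10 minutes and autocorrelation from 0.95 down to 0.5, windowed minus matched is about 0-3 mg/dL at SD 5, 0-6.5 at SD 8 and 1-12 at SD 12.

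**6. One worked case.** Fall from 105 to 58 mg/dL over 75 minutes (drop 47), flat beforehand, lag 10 minutes, SD 8, autocorrelation 0.8. The matched drop is 40.7, short by 47 - 40.7 = 6.3. The windowed drop is 44.3, short by 47 - 44.3 = 2.7. So 6.3 - 2.7 = 3.6 mg/dL of the lag shortfall is masked, and 2.7 stays visible. If glucose had long been falling at that rate before baseline, the matched drop would be 47.0, and the same inflation would appear as overshoot.

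**7. The 60-minute extension.** Ending the window 15 rather than 60 minutes after the test changes the mean by at most about 2 mg/dL, and by under 1 once glucose recovers to 100 mg/dL or more. The main source is the dense minimum near the end of the fall.

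**The case against.** A reader might infer three stronger things; the protocol supports none of them.

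- *The sensor drop is overstated against the reference.* Noise and lag pull in opposite directions, and the protocol gives neither. With strongly autocorrelated errors and a 10-minute lag the windowed drop is still too small. Only the inflation relative to a time-matched sensor drop is established.
- *Lag is hidden.* It can be partly masked in this one comparison. Section 7.2.2.2 also compares nadir times and reports ±2.5-minute paired differences stratified by reference glucose. These do not replace a matched per-subject drop: the paired results are not reported as drops, and the sensor nadir time comes from the same noisy minimum.
- *The 60-minute window is the fault.* It is a reasonable allowance for a delayed sensor nadir and adds little bias once glucose recovers.

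Two further objections carry weight. Each reading already averages 10-second values, so fast noise is damped; if the remaining error is strongly autocorrelated, the inflation may be negligible. And the two drops answer different questions: whether the sensor eventually registered the fall, and whether it was right at that moment. The matched version includes lag, so making it the main one would be a trade-off rather than a correction. Chapter 7 also says that a final analysis plan will supersede section 7.2, so the addition could be made there.

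**Conclusion.** The point holds in limited form. As defined, the sensor drop carries a minimum-search bias that the reference drop has almost none of. Its size ranges from negligible to about 12 mg/dL at the noisiest setting in step 5, set against a fall of roughly 50. That can make a lagging sensor look closer to the reference than it is, or make an unbiased one look as if it overshoots. The direction of the net error cannot be stated from the protocol.

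The figures rest on assumed noise, autocorrelation, lag and recovery. That the minimum search pushes the sensor nadir down does not depend on those values; how far it does so depends on them entirely. The analysis is secondary and descriptive, and the primary hormone comparison is unaffected. This is a cheap improvement, of low severity.

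**What to change.** In section 7.2.2.2, or in the final analysis plan, also calculate each subject's sensor drop from the sensor readings paired within ±2.5 minutes to the reference baseline and the reference nadir. Report it beside the windowed drop in the same plots and summaries, each with a label: the matched drop shows agreement at the same moment, lag included; the windowed drop allows for delay but includes the minimum-search bias. Keep the 60-minute window for the nadir-time analysis.

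The cost is a sentence of text and one extra set of output. It uses the section's own pairing rule and needs no new data. The downside is that the matched drop includes lag, which is why both versions should be shown.

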442 The subjects will be instructed to perform at least 4 blood glucose measurements per day prior to  
443 the CRC admission using the study HGM. The measurements will be performed prior to each meal  
444 and before bed. Additional HGM measurements may also be required for calibration of the device  
445 every 12 hours.

446 **CHAPTER 3**  
447 **SUBCUTANEOUS INSULIN INFUSION TEST**

448  
449 **3.1 CRC Admission**

450 About 6 days (+1 day) following the enrollment visit, subjects will have an inpatient CRC  
451 admission of approximately 18 hours. Subjects will be admitted at approximately 3:00 PM to allow  
452 sufficient time to calibrate the sensors before dinner is provided.

- 453  
454 • Areas where a Guardian RT sensor was worn during the first week will be assessed by study  
455 personnel for any skin irritation.
- 456 • The Guardian RT, HGM, and pump data from the previous week will be reviewed and  
457 changes will be made to diabetes management as needed.
- 458 • Subjects will continue using the Guardian RT sensor last inserted at home. If the sensor is  
459 not functioning properly, a new sensor will be inserted.
- 460 • For subjects of sufficient size, an additional Guardian-RT sensor will be inserted and  
461 calibrated approximately two hours later. An intravenous catheter will be inserted in an arm  
462 vein for collection of blood samples during the admission. The area where the catheter will  
463 be inserted may be numbed with Elamax or EMLA cream prior to catheter insertion.

464  
465 **3.2 Pre-Subcutaneous Insulin Infusion Test**

466 **3.2.1 Blood Glucose Measurements**

467 Blood glucose measurements will be made using the study HGM at bedtime, 12 a.m., 3 a.m., 6 a.m.,  
468 and 7 a.m. to ensure the blood glucose level will be above 110 mg/dL at the time of the start of the  
469 test.

- 470 • Oral carbohydrates or a correction dose of insulin may be given if the subject's glucose level  
471 is too low or too high.
  - 472 ○ Glucose level will be repeated 30 min later if treatment was given for low glucose or  
473 90 minutes later if a bolus insulin dose was given for high glucose.
  - 474 ○ Glucose will be considered to be low if less than 80 and will be treated with 15  
475 grams of carbohydrates.
  - 476 ○ Glucose will be considered to be high if above 200mg/dl at midnight, 170mg/dl at 3  
477 a.m. and 150 mg/dl at 6 a.m. A correction dose of insulin may be given for high  

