### 502 **3.3.1 Blood Glucose Measurements**

504 The clinical centers either will use reinfusion of blood or will discard blood with each blood draw,  
505 depending on the standard practice at each center's CRC. The blood draws will be performed by  
506 the method in standard use at the CRC. The blood samples will be sent to a central lab.

507  
508 Glucose concentrations will be checked on the study HGM every 15 minutes with venous blood  
509 until the glucose level reaches  $\leq 100$  mg/dL. Thereafter, the study HGM will be used to check the  
510 glucose levels in 5-10 minute intervals with venous blood depending on the rate of fall of the  
511 glucose level until the end of the study. Subjects and parents will be masked to the results of the  
512 glucose testing during the subcutaneous insulin infusion test in an attempt to eliminate bias when  
513 answering questions regarding symptoms of hypoglycemia.

- 514 ○ Blood samples will be collected for laboratory determination of glucose and hormone  
515 concentrations at baseline when the subject's glucose level is between 95 and 110 mg/dL (in  
516 duplicate) and when the glucose levels are <90, <80, <70, and <60 mg/dL.
- 517 ○ Parents (and subject if appropriate) will be asked questions regarding symptoms of  
518 hypoglycemia each time the glucose level is checked with the study HGM.
- 519 ○ Once the endpoint is reached (the first time the glucose is <60 mg/dL using the study HGM),  
520 the basal rate will be returned to normal, the subjects will be treated with intravenous  
521 glucose and breakfast will be provided. An additional blood sample will be collected for  
522 laboratory determination of glucose and hormone concentrations 15 minutes following the  
523 treatment with intravenous glucose.

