### 524 **3.3.2 Blood Samples for Hormone Concentrations**

526 Blood samples will be collected for epinephrine, norepinephrine, cortisol, glucagon and GH at  
527 baseline when the subject's glucose level is between 95 and 110 mg/dL (in duplicate) and when the  
528 glucose levels are <90, <80, <70, and <60 mg/dL. A final sample will be collected 15 minutes  
529 following the treatment with intravenous glucose when the subjects glucose level is <60 mg/dL.

530  
531 As permitted by weight, additional samples may be collected for possible later analysis of  
532 pancreatic polypeptides, IGF BP1, insulin and others each time a sample is collected for glucose  
533 and hormone concentrations.

534  
535 All samples collected for hormones will be collected, frozen, and shipped to the central laboratory  
536 for storage. A determination will be made once the primary outcome is known regarding which  
537 samples to process.

538

539 **3.4 Post-Subcutaneous Insulin Infusion Test**

540 Once the study endpoint is reached (the first time the glucose is <60 mg/dL using the study HGM),  
541 the basal rate will be returned to normal and the subjects will be treated with intravenous glucose.  
542 An additional blood sample will be collected for laboratory determination of glucose and hormone  
543 concentrations 15 minutes following the treatment with intravenous glucose. Subjects will then be  
544 given breakfast and discharged. Prior to discharge, the sensor(s) will be removed and downloaded.  
545 The subject's insulin pump will be downloaded if possible.

546

547 **3.5 Daily Activities**

548 Subjects will be permitted to perform their usual indoor activities during the hospitalization, except  
549 during the subcutaneous insulin infusion test where they will be restricted to bed.

550

551 **3.6 Diet**

552 The prescribed diet will be at the discretion of the investigator.

553 **CHAPTER 4**  
554 **EVALUATION OF CONTINUOUS GLUCOSE MONITORS**  
555

556 **4.1 Overview**

557 The accuracy of the Guardian-RT will be evaluated during the inpatient phase.  
558

559 **4.2 Inpatient Accuracy Evaluation**

560 The inpatient stay is described in the prior chapter.  
561

562 At the start of the admission, the following will be done:

- 563 • Areas where a Guardian RT sensor was worn during the previous week will be assessed for  
564 skin reactions.
- 565 • Subjects will continue using the Guardian RT sensor inserted prior to the admission.

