1011  
 1012 Sensitivity to detect hypoglycemia will be assessed by calculating the percentage of subjects with a  
 1013 sensor value <70, <60 and <50 mg/dL between baseline and 60 minutes following completion of the  
 1014 subcutaneous insulin infusion test. A similar sensitivity analysis for hyperglycemia will be done for  
 1015 those subjects with a reference glucose >200 mg/dL during the post-dinner blood draws.

1016  
1017 During home use of the Guardian RT, analysis of hypoglycemia detection will be based on clinical  
1018 events rather than individual points and will allow margins of error for both time (30 min) and  
1019 glucose (10 mg/dL). Multiple glucose values below the hypoglycemic threshold (e.g., <70 mg/dL)  
1020 within 30 minutes will be analyzed as a single event. Sensitivity will be defined as the percentage  
1021 of reference events for which the sensor alarmed within 30 minutes of the first low reference value.  
1022 The false positive rate will be defined as the percentage of sensor events for which all reference  
1023 values within 30 minutes of the first low sensor reading were above the hypoglycemic threshold.  
1024 Events where the sensor was always within  $\pm 10$  mg/dL of the reference, but on the opposite side of  
1025 the hypoglycemic threshold (e.g., sensor=68/reference=72) will not be counted as either a success  
1026 or a failure and will be excluded from the calculation. Parallel analyses will be conducted for  
1027 hyperglycemic episodes.  
1028  
1029

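### The inpatient hypoglycemia sensitivity in section 7.2.2.2 is not a sensitivity as written, because its denominator is not limited to subjects whose reference glucose fell below each cut-off; this is serious at <50 mg/dL

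*Protocol*

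**What the plan says.** **Inpatient rate.** Section 7.2.2.2 states: "Sensitivity to detect hypoglycemia will be assessed by calculating the percentage of subjects with a" "sensor value <70, <60 and <50 mg/dL between baseline and 60 minutes following completion of the" test. The next sentence applies a similar analysis to hyperglycemia, but only in "those subjects with a reference glucose >200 mg/dL during the post-dinner blood draws". The same section names the inpatient reference: "Laboratory glucose measurements will be used as the reference during the CRC Admission for" judging the Guardian-RT.

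**How low subjects go.** Section 3.3.1 ends the descent on a bedside meter value: "Once the endpoint is reached (the first time the glucose is <60 mg/dL using the study HGM"), after which intravenous glucose is given. Section 3.3 lets the investigator stop a test that has not reached this endpoint within 3 hours. Section 5.5.1 ends it early for marked symptoms at glucose above 60 mg/dL.

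**Home rates.** Section 7.2.2.2 bases sensitivity on reference events and the false positive rate on sensor events, with declared margins of 30 minutes and 10 mg/dL. An event in which the sensor stayed within 10 mg/dL of the reference but on the other side of "the hypoglycemic threshold (e.g., sensor=68/reference=72) will not be counted as either a success" or a failure, and it leaves the calculation.

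**Timing.** Section 3.1 gives an "admission of approximately 18 hours. Subjects will be admitted at approximately 3:00 PM to allow" time for sensor calibration before dinner. Section 3.3 starts the test at about 8:00 a.m. and expects 1.5 to 2 hours. Under section 3.4, after the post-treatment sample, subjects are "given breakfast and discharged. Prior to discharge, the sensor(s) will be removed and downloaded".

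**The concern.** A sensitivity is the share of truly positive cases that the device detects. Here the hypoglycemia denominator is every tested subject, whether or not the reference crossed the cut-off. A subject who never fell below 50 mg/dL lowers the figure if the sensor correctly stays above 50, and raises it if the sensor reads falsely low. The statistic can therefore reward error. The hyperglycemia sentence shows that the authors had the needed condition in hand.

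Accuracy of the Guardian-RT during hypoglycemia is secondary objective 3 (section 1.2), and a percentage labelled sensitivity is likely to be quoted as one.

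Two smaller matters concern the same analyses. The home exclusion removes near-threshold disagreements but keeps equally close agreements, so it works in one direction. And the sensor window for the inpatient rate, the nadir and the lag runs to 60 minutes after the test, which the stated length of stay does not cover.

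**Working it through.** The protocol gives no figure for any of these rates, so there is none to reproduce. It also gives no nadir distribution and no sensor error. All values for these below are assumptions.

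**1. What the inpatient statistic estimates**

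Let f be the share of subjects whose reference goes below the cut-off, s the true sensitivity, and q the chance of a sensor value below the cut-off when the reference is not below it. The stated percentage is

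f × s + (1 − f) × q.

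It equals s only if f = 1 (or if q = s). A perfect sensor (s = 1, q = 0) scores f.

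With s = 0.80 and q = 0.05 to 0.20:

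| Cut-off (mg/dL) | Assumed f | Stated statistic | True sensitivity |
|---|---|---|---|
| <70 | 0.90 to 1.00 | 0.73 to 0.80 | 0.80 |
| <60 | 0.60 to 0.95 | 0.50 to 0.77 | 0.80 |
| <50 | 0 to 0.20 | 0.05 to 0.32 | 0.80 (undefined if f = 0) |

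Example at <50 with f = 0.20 and q = 0.20: 0.20 × 0.80 + 0.80 × 0.20 = 0.32.

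**2. Size at <50 mg/dL**

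Assume a normal true nadir with mean m = 55 or 57 and SD d = 3 or 5 mg/dL, and one unbiased sensor reading at the nadir with error SD e. Then P(reading <50) = Φ((50 − m)/√(d² + e²)).

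| m, d | Perfect (e = 0) | e = 8 | e = 12 |
|---|---|---|---|
| 57, 3 | 1.0% | 20.6% | 28.6% |
| 57, 5 | 8.1% | 22.9% | 29.5% |
| 55, 3 | 4.8% | 27.9% | 34.3% |
| 55, 5 | 15.9% | 29.8% | 35.0% |

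The perfect sensor scores about 1-16% and the noisy one 21-35%. In every row the worse device scores higher. The protocol takes any reading over a window, not one reading, which gives a noisy sensor more chances to read low.

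**3. The home exclusion**

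Simple arithmetic: with 60 of 100 events detected, the rate is 60%. If 10, 20 or 30 of the 40 misses lie within the tolerance, it becomes 60/90 = 67%, 60/80 = 75% or 60/70 = 86%. As an extreme, take a sensor that always reads 9 mg/dL high, with reference events uniform on 45-70 and a threshold of 70. It detects events below 61, (61 − 45)/25 = 64%, but all its misses are dropped and it scores 100%.

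With random error the size depends on how the rule is modelled (reference uniform on 45-70, alarm set at 70):

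| Model | Error SD 12, no bias | Error SD 8, bias +5 |
|---|---|---|
| One sensor-reference pair per event | 81% to 86% | 75% to 83% |
| 13 five-minute readings, all must be within 10 mg/dL | adds 0 to 0.2 points | adds 0 to 1.3 points |
| 13 readings, tolerance judged on one | adds about 0.2 to 1.5 points | adds about 0.9 to 3.8 points |

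The last two rows assume a constant reference and error autocorrelation of 0.8 to 0.98. In single-pair simulations with error SD 10-20, bias 0 or +10 and three glucose distributions, the false positive rate fell by about 2.5 to 7 points (for example 14.0% to 8.2%).

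**4. The clock**

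- Stay: 15:00 + 18 h = 09:00.
- Test end: 08:00 + 1.5 to 2 h = 09:30 to 10:00.
- Sensor window closes: 10:30 to 11:00, or 08:00 + 3 h + 1 h = 12:00 after a 3-hour test.

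The window closes 1.5 to 3 hours after the nominal end of the stay.

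**The case against.** **The test induces hypoglycemia by design.** It aims to take each child to a meter value below 60, so the rule could be read as the share of children given induced hypoglycemia whom the sensor showed as low, at three read-out levels. The post-dinner rise has no glucose target, so a restriction may be needed only there. This has force at <70, where anyone who reaches the endpoint has passed 70 on the meter. At <60 it is weaker: tests may stop above 60, and the endpoint is a meter value while the reference is laboratory glucose. At <50 it fails, because the design does not aim there.

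**Other analyses would expose a falsely low sensor.** Section 7.2.2.2 also plans paired differences and ISO rates by reference glucose, Bland-Altman plots, and sensor-versus-reference drops and nadir times. Chapter 7 says that a final analysis plan will supersede section 7.2. This limits the damage, but does not make the stated percentage a sensitivity.

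**Home rates.** A reader might infer that these do not measure detection either, or that the exclusion removes only failures. The documents do not support that. The denominators are right and the tolerance is declared in advance. Section 1.1.2.1 makes alarms user-adjustable, so an alarmed event with the sensor just above the threshold would be a success that is also dropped. The home reference is a meter with its own error, so counting 68 against 72 as a sensor failure is debatable. The single-pair effect of 5 to 8 points also ignores the requirement that the sensor be within tolerance throughout the event. What stands is that the rule is one-sided.

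**Timing.** A reader might infer that nadir and lag data will be cut off. No section says that sensors come off within 60 minutes: a 15-minute sample and breakfast come first, and the times are approximate. Truncation is possible, not shown.

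**Conclusion.** The inpatient hypoglycemia sensitivity should be redefined. That it lacks a reference condition is plain from the text and needs no assumption. Its size does: under a nadir of mean 55-57 and SD 3-5 mg/dL, the <50 figure is about 1-16% for a perfect sensor and 21-35% for one with error SD 8-12. The fault is possible at <60, depending on how many tests stop early and on meter-laboratory disagreement, neither of which the protocol quantifies, and minor at <70.

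Two secondary points hold in limited form. The home exclusion makes the rates somewhat optimistic, by an amount that depends on assumptions and may be under one or two points for sensitivity under the event rule. The 18-hour stay does not fit the 60-minute post-test window on the protocol's own times.

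All of this concerns a secondary objective. The primary hormone comparison is untouched.

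**What to change.** 1. In section 7.2.2.2, or in the final analysis plan, define inpatient sensitivity at each cut-off among subjects with at least one central-laboratory glucose below that cut-off during the test. Report the number with each percentage. Omit <50 mg/dL if almost no one qualifies.
2. Report the home sensitivity and false positive rate with and without the near-threshold exclusion, together with the number of events excluded.
3. Reconcile the length of stay in section 3.1, the test duration in section 3.3 and the sensor removal in section 3.4 with the 60-minute sensor window in section 7.2.2.2.

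Items 1 and 2 are changes of analysis wording and need no new data. Their cost is smaller denominators at the lower cut-offs and an extra column for the home rates. Item 3 is a text reconciliation; if it is resolved in favour of the full window, it may mean up to about an hour more sensor wear for some subjects.
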